Part 2: Treatment with CBT-I or Health and Wellness. Participants will be recruited for Part 2 until 60 participants are screened eligible and have agreed to participate. We anticipate screening 190 records and participants in order to recruit 60 participants for Part 2. Participants will be randomized to either the CBT-I (treatment) condition or the Health and Wellness (control) condition. Procedures for Part 2, Treatment are otherwise the same as in Phase 1, Treatment, with the exception that we will not pose open-ended questions to participants about recommendations for changes to the treatment.

Time Point 2 Assessment Battery. The Time Point 2 Assessment Battery will follow the same assessment procedures as in Phase 1. Approximately two weeks prior to the Time Point 2 (Post) Assessment date, participants may be given an Actiwatch and will be given sleep diaries to complete. Participants will be paid \$30 for participation in the post quantitative assessment battery. If a Veteran is unable to complete the study assessment at a VAMC and does not wish to complete the full assessment battery via telephone, then we will offer to conduct the 7-item Insomnia Severity Index (ISI) measure over the phone and strongly encourage the Veteran to choose a confidential location for this questionnaire.

Time Point 3 (Follow up) Assessment Battery. At 3 months following the intervention, participants will complete the Time Point 3 (Follow Up) Assessment Battery used in Time Points 1 and 2. Approximately two weeks prior to the Time Point 3 (Follow Up) Assessment date, participants may be given an Actiwatch and will be given sleep diaries to complete. Participants will be paid \$30 for participation in the follow up quantitative assessment battery. If a Veteran is unable to complete the study assessment at a VAMC and does not wish to complete the full assessment battery via telephone, then we will offer to conduct the 7-item Insomnia Severity Index (ISI) measure over the phone and strongly encourage the Veteran to choose a confidential location for this questionnaire.

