Qualitative Interview: Those participants randomized to the CBT-I intervention may also be invited to complete an additional interview shortly after completing the treatment sessions. Up to 30 participants will be asked to complete qualitative interviews. This interview will include questions about their experiences while in CBT-I, as well as their opinion of how this treatment could be improved upon. We will also ask for their input to help us think about how to best offer this intervention to others. The interview will take about 1 hour and will be audio recorded. Participants who complete this additional interview will be paid \$40 for participation in the qualitative interview.

OPTION FOR TELEPHONE-BASED SESSIONS:

For the intervention sessions, the qualitative interview, and the self-report surveys administered at all timepoints, if participants are unable to participate in person, they will have the option of completing these activities by phone. Participants completing the self-report measures or qualitative interviews by phone will be mailed their participation compensation funds. As there is one assessment measure (MATRICS) that must be completed in person, participant compensation for assessment time points will be divided if they complete self report measures over the phone (\$20) and the MATRICS in person (\$10). Due to COVID-related safety issues with having participants complete the MATRICS in person, any participants who had a post or follow up in the COVID era will not be completing the MATRICS or receiving the corresponding \$10 for participating in the MATRICS. We will use VA email to communicate with veteran participants during the RCT in order to send electronic copies of resources, blank worksheets, and/or response cards for participants to use during phone sessions. We will only send these materials at the veteran's request and staff will discuss proper procedures for communication via email with the veterans ahead of time to ensure understanding. The emails will also include a clear statement that no completed forms or personal identifying information should be sent to staff via email correspondence, and that any emails to veteran participants will be deleted upon receipt to help ensure security. For instance,

Hello.

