* Describe any additional participant requirements:

ID: VIEW4E0280585B400 Name: v2_Study Procedures

Sample Size and Data Analysis V2

Sample Size and Data Analysis

HP-00074686

If you uploaded a separate research protocol document in the 'Research Protocol' page, cite the applicable section and page numbers from that document in the answer boxes below.

* Provide the rationale and sample size calculations for the proposed target population:

Phase 1 (Acceptability Trial): Due to the estimated rates of insomnia and sleep apnea in prior literature on Veterans with psychotic disorders, we have determined the sample size of 20 to be an appropriate number to attain a final sample size of 6. We determined the sample size of 6 to be feasible for the purpose of an acceptability

Phase 2 (RCT): Due to the estimated rates of insomnia and sleep apnea in prior literature on Veterans with psychotic and bipolar disorders, we have determined the sample size of 190 to be an appropriate number to attain a final sample size of 60. After considering time and resources available with this CDA-2, we believe it will be feasible to randomize 30 individuals per condition, thus the total sample size of 60. With 25% anticipated loss to follow-up at PT, we anticipate outcome assessments at PT for approximately 22-23 participants per condition. We expect 35% loss to follow-up at the follow-up visit, leaving 19-20 per condition). With the anticipated 22-23 per condition with complete data at post-treatment, power is estimated to be at least .80 for detecting between "medium" and "large" effect sizes (d=.60) with the ANCOVA analysis, assuming BL to PT correlation in the response variable is r=0.7. Assuming r=0.6, the detectable effect size increases to d=.67 (with power=.80). Up to 30 participants within the CBT-I condition will be asked to complete the qualitative interview. This will allow us to gain a rich understanding of the variety of experiences participants within the CBT-I condition have had with the treatment.

* Provide the plan for data analysis. Include in the description the types of comparisons that are planned (e.g., comparison of means, comparison of proportions, regressions, analysis of variance, etc.), which is the primary comparison/analysis, and how the analyses proposed will relate to the primary purposes of the study:

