Specific Aim 3, Hypotheses 2a-b (H2a,b). Compared to a general Health and Wellness Intervention, CBT-I will show significant a) decreases in insomnia symptoms (as measured by the ISI) and b) increases in functioning (as measured by the VR-36). Analysis: For the two outcomes for H2a and H2b we will use the mixed model described above. For example, to assess the effect of CBT-I on insomnia severity as measured by variable Y= ISI, the model will be: Y_j=\beta_0+\beta_1 "Y"_1+\beta_2 P"T + β_3 "FU + " β_4 "CBT-I +" β_5 "CBT-I POST + " β_6 "CBTI FU + " e_j , where j = 2, 3 are the PT and FU assessment points respectively, Y1 is the baseline value, and POST, FU, and CBT-I are indicator variables for the PT and FU time-points and the CBT-I intervention condition (versus the control condition). β_5 in the model, equal to the group differences at PT (i.e. treatment effect) and FU, will be tested against the Null hypothesis that that β_5=0. As mentioned above an important out-of-balance covariate and potential confounder could also be included in the model.

Secondary Aims. In secondary analyses, actigraphy outcomes will include the length of time between target bedtime (via sleep log information) and sleep onset (sleep latency), and the number of awakenings after sleep onset. The right-hand-side of the model for Specific Aim 3 will also be used for these outcomes, however the type of longitudinal model may differ. For example, a Poisson or Negative Binomial model using generalized estimating equations (GEE) would likely be a better fit for testing the treatment effect on the count variable, number-of-awakenings.

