 - · Coping Strategies Scale
 - · Difficulties in Emotion Regulation Scale
 - · Brief Irritability Test
 - Illness Management and Recovery Scale: Consumer Self-Rating
 - PROMIS Fatigue measure
 - Functional Outcomes of Sleep Questionaire-10
 - Motivation and Pleasure Scale
 - World Health Organization Disability Assessment Schedule (WHO-DAS 2.0)
 - WHO-DAS-Insomnia
 - Veterans RAND 36-item Health Survey (VR-36)
 - Veterans RAND Health Survey-Insomnia Items
 - · Eating/physical activity readiness to change items
 - Smoking History Form (SHF)
 - Fagerstrom Tolerance Scale (FTS)
 - · Ready Willing and Able Smoking questionnaire
 - ASI/AUDIT Questionnaires
 - · Suicide Behaviors Questionnaire-Revised
 - Brief Resilience Scale
 - · Glasgow Sleep Effort Scale
 - · Satisfaction with Treatment Form
 - · Iowa Sleep Disturbances Inventory-Unusual Experiences Subscale,
 - · Sleep Diary (CSD-Core) with instructions
 - Sleep Diary (CSD-Core) Trial we included this modified form of the Sleep Diary (CSD-Core) to include more detailed information regarding when participants removed the Actiwatch device.
 - Sleep Diary (CSD-Core) Trial with medications- we included this modified form of the Sleep Diary (CSD-Core) to include more detailed information regarding when participants removed the Actiwatch device and medications used to help with sleep.
 - Sleep Diary (CSD-Core) Eligibility we included this modified form of the Sleep Diary (CSD-Core) to include more detailed information regarding when participants removed the Actiwatch device and when participants wore the WatchPAT device for home sleep screening CBT-I Treatment Components Adherence Scale (TCAS)
 - STOP-BANG Sleep Apnea Measure (STOP-BANG) · Participant Application of Sleep Strategies
 - Sleep Knowledge Check
 - International Restless Leg Syndrome Screen and Measure

* Upload a copy of all questionnaires/surveys:

Created	Modified Date
11/5/2018 4:09 PM	1/7/2019 11:10 AM
4/12/2017 11:42 AM	12/13/2018 10:37 AM
5/8/2018 9:23 AM	5/8/2018 9:23 AM
3/29/2018 8:34 AM	5/8/2018 9:17 AM
3/29/2018 8:31 AM	5/8/2018 9:16 AM
3/29/2018 8:35 AM	5/8/2018 9:16 AM
3/29/2018 8:33 AM	5/8/2018 9:15 AM
3/30/2018 10:36 AM	5/8/2018 9:13 AM
3/29/2018 8:30 AM	5/8/2018 9:12 AM
12/12/2017 10:19 AM	5/8/2018 9:11 AM
	11/5/2018 4:09 PM 4/12/2017 11:42 AM 5/8/2018 9:23 AM 3/29/2018 8:34 AM 3/29/2018 8:31 AM 3/29/2018 8:35 AM 3/29/2018 8:33 AM 3/30/2018 10:36 AM 3/29/2018 8:30 AM

Name	Created	Modified Date

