1.2	* Provide exact text of all proposed advertisement(s): Are you bothered by sleep problems? We are looking for Veterans (age 18 and older) who are dissatisfied wi mental illness (ex. Schizophrenia Disorders, Bipolar Disorder, or Depression with Psychosis) to partake in a r conducted at the Baltimore/Perry Point VA. Please call [name] at [contact] to see if you are e is conducted under [name]., VISN 5 Mental Illness Research, Education, and Clinical Cent number below and call us for more details!	esearch study on Insomnia Tre ligible. You will be paid for you	eatment. Research will be reparticipation. This research
1.3	* Upload advertisement(s) here:		
	Name	Created	Modified Date
	advertisement_CBT-I_PPVA- [name] 1.03.19.pdf(0.02)	12/12/2017 10:10 AM	1/7/2019 9:43 AM
	advertisement_CBT-I_BaltimoreVA- [name] 1.03.19.pdf(0.02)	12/12/2017 10:10 AM	1/7/2019 9:43 AM
	BT-I Handouts 1.03.19.pdf(0.02)	6/13/2018 4:15 PM	1/7/2019 9:43 AM

ID: VIEW4E0BCE82B8C00 Name: v2_Advertising Detail

Research Related Risk V2

Research Related Risks

If you uploaded a separate research protocol document in the 'Research Protocol' page, cite the applicable section and page numbers from that document in the answer box below.

- *Individually list each research-related risk, using a separate line for each. Next to each risk, delineate the likelihood/seriousness of the risk, and the provisions for minimizing the risk:
 - (1) Some participants may feel embarrassed or uncomfortable when they have to answer questions that they may feel are personal (small likelihood, low degree of seriousness). To minimize this risk, participants are told before each assessment the nature of the questions being asked and are told to answer honestly but to feel free to not answer questions that make them feel uncomfortable. Study interviewers are trained to talk about personal material with patients and to engage in discussions in a supportive and empathic and nonjudgmental way.
 - (2) Participants may feel bored or tired due to the length of time required to complete the interview/assessments (moderate likelihood, low degree of seriousness). To address this risk, participants will be given the option of scheduling the assessments over two appointments on two different days. In cases in which a participant is tired or bored during an assessment, he/she will be offered breaks or allowed to end the assessment and finish the remainder on another day.

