 - (3) Distress During Assessments (small likelihood, low degree of seriousness). Before consent and before and during each data collection, participants are informed that they are free to decline to answer any interview question(s) or to discontinue the interview at any time. If participants feel uncomfortable or fatigued, or seem so to the RA, they are encouraged to take a break and continue again later, or to stop the interview. In our research with people with serious mental illnesses over the past several years, few research participants have expressed distress from participating in the assessments and interviews. Nonetheless, all RAs have been trained to stop the interview if a participant becomes distressed and will have the resources needed to assist him/her in obtaining the level of support or assistance they require, including
 - (4) Participants may feel some discomfort with discussing their cognitions related to sleep or with restructuring their nighttime routines to accommodate the activity structuring involved in CBT-I (moderate likelihood, low degree of seriousness). Likewise, participants may feel some discomfort with discussing their health behaviors in the Health and Wellness intervention. However the CBT-I and the Health and Wellness intervention protocols are not generally considered unpleasant and more severe reactions are uncommon based on prior studies using CBT-I and Health and Wellness.

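### The short phone fallback at post-treatment and follow-up offers the ISI (H2a) but not the VR-36 (H2b); adding the VR-36 after it is a cheap, modest gain

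*Combined protocol and SAP*

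**What the plan says.** Study Procedures, Phase 2, Part 2, uses the same fallback sentence for Time Point 2 (post-treatment, PT) and Time Point 3 (3-month follow-up, FU). It applies to a Veteran who cannot be assessed at a VA medical center and who "does not wish to complete the full assessment battery via telephone". For that person, "then we will offer to conduct the 7-item Insomnia Severity Index (ISI) measure over the phone". No other measure is named.

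Sample Size and Data Analysis (Specific Aim 3, Hypotheses 2a-b) assigns the ISI to H2a and the VR-36 to H2b and fits the same mixed model to each.

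Three other places bear on the point:

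- Under the option for telephone-based sessions, participants who cannot come in may do the self-report surveys remotely at every time point: "they will have the option of completing these activities by phone". The VR-36 is in the survey list.
- Research Related Risks allows partial completion. Item 1 tells participants to "feel free to not answer questions that make them feel uncomfortable", item 2 allows an assessment to be split over two days, and under item 3 "participants are informed that they are free to decline to answer any interview question(s) or to discontinue the interview at any time".
- The sample size section expects 25% loss at PT and 35% at FU from 30 per arm. It then begins its power claim "With the anticipated 22-23 per condition with complete data at post-treatment", without naming the outcome.

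**The concern.** The trial has two efficacy hypotheses, and the last-resort contact secures the outcome for only one of them. The general phone option makes the VR-36 feasible remotely, but fallback users have already declined the full phone battery, and the only thing the plan then offers them is the ISI. A partial set is permitted but not prompted, so whether anyone collects the VR-36 is left to the staff member on the call.

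At stake is a little H2b information at PT and FU. The mediation analysis (EA3) needs both outcomes and loses the same people. With about 22-23 per arm expected at PT and 19-20 at FU, each person recovered has a visible though small effect on power.

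**Working it through.** **Inputs from the sample size section.** 30 per arm. Retained at PT: 30 × 0.75 = 22.5 (stated as 22-23). Retained at FU: 30 × 0.65 = 19.5 (stated as 19-20). ANCOVA with d=.60 at baseline-to-PT correlation r=.7, or d=.67 at r=.6. Stated power is at least .80.

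**Assumed.** Two-sided 5%, because no alpha is stated; one-sided 5% gives .87-.89 and does not match. The plan's d and r are applied to the VR-36, and at FU as well.

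**Reproducing the plan's figure.** By the normal approximation, power = Φ(d / √((1−r²)·2/n) − 1.96).

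- r=.7, d=.60, n=22.5: 0.60 / √(0.51 × 2/22.5) = 0.60/0.2129 = 2.818, and Φ(0.858) = .805. Over n=22-23 the range is .796-.813.
- r=.6, d=.67, n=22.5: 0.67 / √(0.64 × 2/22.5) = 0.67/0.2385 = 2.809, and Φ(0.849) = .802.
- The effects detectable with 80% power at n=22.5 are .597 and .668, which round to the stated .60 and .67.

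The plan's figures reproduce. The noncentral t with one covariate (ncp = d/√(1−r²) × √(n/2), df = 2n−3) runs about two points lower: .777-.795 for r=.7, with .786 at n=22.5. It is used below because the samples are small. Starting under .80 reflects the method and is not an error in the plan.

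**Case A: the 22-23 with complete data exclude ISI-only respondents (the ordinary reading).** Planned H2b power is unchanged, and anyone recovered adds to it. With k people per arm recovered, r=.7 and d=.60:

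| k | PT n | PT power | PT detectable d | FU n | FU power | FU detectable d |
|---|---|---|---|---|---|---|
| 0 | 22.5 | .786 | .611 | 19.5 | .723 | .658 |
| 1 | 23.5 | .804 | .597 | 20.5 | .746 | .641 |
| 2 | 24.5 | .821 | .584 | 21.5 | .767 | .625 |
| 3 | 25.5 | .836 | .572 | 22.5 | .786 | .611 |

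Over the plan's whole ranges (22-23 and 19-20), power rises at PT from .78-.80 to .80-.81, .81-.83 and .83-.84, and at FU from .71-.74 to .74-.76, .76-.78 and .78-.80. With r=.6 and d=.67 the PT midpoint series is .784, .802, .818, .834 and the FU series is .721, .743, .764, .784.

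**Case B: ISI-only respondents are counted inside the 22-23.** H2b is then analysed on 22.5 − k at PT. For k = 1, 2, 3 power is .767, .746, .723 (normal approximation .787, .767, .746). If those people do give the VR-36 at FU, the joint PT/FU model recovers a little. With 19.5 per arm seen at both visits, 3 at PT only, k moved to FU only and all pairwise correlations .7 (assumed), the effective PT n is 21.66, 20.81, 19.94 and power is .770, .752, .733. Varying the PT-FU correlation from .6 to .8 moves the k=3 value between .726 and .746.

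**The case against.** The best reply is that this is a preference. A seven-item last resort for someone who has just declined a battery whose surveys alone take about 90 minutes is a sensible retention choice in a small feasibility trial. Surveys may already be done by phone and sessions may be split over two days, so a Veteran deterred by length has a route that includes the VR-36. Those who still decline are the least likely to accept 36 more items. No uptake figure exists. On the ordinary reading, the people recovered come from the 7-8 per arm without complete PT data (30 minus 22-23), so three per arm would be about 40% of them, which is optimistic. EA3 is exploratory and conditional on H2b. Data collection may be nearly over: the payment section describes COVID-era phone payments in the past tense.

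Much of this stands, and it limits the size of the gain: one person per arm is worth about two points. It does not close the gap. Neither the general phone option nor split sessions makes any further offer to a person who has already declined the full phone battery. Declining the whole battery is also not the same as declining one questionnaire, and refusal of the VR-36 would leave the secured ISI intact.

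**Conclusion.** The point holds as an optional improvement. The fallback explicitly secures the H2a outcome and makes no offer of the H2b outcome, at both visits. Putting the ISI first is reasonable and is not disputed.

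Each person recovered per arm adds about 1.5 to 2 points of H2b power at PT and about 2 at FU, and less if some refuse the VR-36. This rests on an assumed one to three people per arm, two-sided 5%, and the plan's d and r holding for the VR-36. The stated power is not shown to be wrong. H2b would fall below plan only if ISI-only respondents are counted among the 22-23, by an amount the documents do not fix.

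**What to change.** In the two fallback sentences (Time Points 2 and 3), conduct the ISI first, then offer the VR-36 in the same call or a second short call, with the Veteran free to refuse. In the sample size section, say whether the 22-23 with complete data exclude ISI-only respondents. In the results, give the numbers with the ISI and with the VR-36 separately, by arm and visit.

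The cost is a short amendment to two identical sentences and one optional 36-item questionnaire for fallback users; the documents give no separate time for the VR-36. It may also need VR-36 response cards for the call, an updated phone script, and a line on payment for a partial set, since the plan sets $20 for the phone self-report measures and names no partial amount. The change helps only visits still to come. The form is dated 4/19/22, so if collection has finished, what remains is to clarify who is counted in the 22-23 and to report the denominators by outcome.

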Phase 2 (RCT): Specific Aim 3, Hypothesis 1 (H1). CBT-I intervention feasibility will be demonstrated by adequate rates of recruitment, initial intervention engagement, attendance at intervention sessions, and therapist fidelity. Analysis: We will use descriptive statistics to summarize the feasibility of CBT-I by: Calculating (a) the rate of recruitment (# consented divided by # approached and # randomized divided by # consented) and compare these to recruitment goals; (b) the percent who engaged in treatment (% of randomized who attend first 3 sessions), median (and inter-quartile range [IQR]) of the total number of sessions attended and treatment dropout rates (# who dropped out prior to completing treatment divided by # who engaged); (c) the median (and IQR) of the number of reminders and outreach contacts made for each participant; (d) the mean (and SD) of the CBT-I Treatment Components Adherence Scale assessed at post-treatment; and (e) the percent of participants who turned in completed sleep logs and percent of the total number of treatment sessions in which completed sleep logs were turned in. To assess therapist fidelity to CBT-I, we will compute percent of sampled sessions in which interventionists were adequately adherent as defined by the rollout criteria of the VA CBT-I EBP of an average rating equal to 2 ("satisfactory"), in addition to no items at a score of 0 ("poor") on the Assessment Competency Rating Scale and the Therapy Competency Rating Scale. For the Health and Wellness condition, we will also compute percentages of sampled sessions with adequate adherence on our Health and Wellness Therapist Adherence and Competence rating scales with parallel criteria for adequacy (i.e. average score equal to "acceptable" and no items scored as "unacceptable").

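### Two descriptive feasibility rules under Hypothesis 1 are wrong as written: the dropout numerator is not limited to engaged participants, and the CBT-I fidelity cut is an equality where a floor appears to be meant (minor)

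*Combined protocol and SAP*

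**What the plan says.** Both rules are in the Specific Aim 3, Hypothesis 1 paragraph of the Sample Size and Data Analysis section. Feasibility is to be shown by "adequate rates of recruitment, initial intervention engagement, attendance at intervention sessions, and therapist fidelity", summarised with descriptive statistics.

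**Dropout.** Engagement is "the percent who engaged in treatment (% of randomized who attend first 3 sessions"). The next measures in that item are the median number of sessions attended and "treatment dropout rates (# who dropped out prior to completing treatment divided by # who engaged"). The numerator carries no restriction to those who engaged, and no other section adds one. The Study Procedures section gives about 10 sessions and lets the number vary with what each participant needs for insomnia symptoms to fall. It does not say what counts as completing treatment.

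**Fidelity.** The measure is the "percent of sampled sessions in which interventionists were adequately adherent", with adequacy "as defined by the rollout criteria of the VA CBT-I EBP of an average rating equal to 2", the score labelled satisfactory, "in addition to no items at a score of 0", labelled poor. The Health and Wellness arm gets "parallel criteria for adequacy (i.e. average score equal to" the acceptable label, with no item rated unacceptable. The documents state neither the top score nor the number of items for any of these scales.

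**The concern.** A dropout rate should count the same people above and below the line. Here, someone who leaves after one session has dropped out before completing treatment but never engaged, so that person can be in the numerator and not in the denominator. The neighbouring ratios are nested, for example "randomized divided by # consented" and engaged over randomized; this one is not. The reported rate therefore depends on whether the analyst follows the text or supplies the missing restriction, and a published figure would not show which was done.

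The fidelity cut raises a different problem. A pass rule for adequate adherence should let a better-rated session pass. An exact equality passes only sessions that average the cut itself. Therapist fidelity is one of the four named feasibility criteria, so its pass rule should be right. Dropout is a supporting description and not a named criterion.

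**Working it through.** The documents give no numerical value for the dropout rate or the fidelity percentage, so there is no plan figure to reproduce. The check is on the rules.

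**Dropout: general form.** Let R be the number randomized to an arm, E the number engaged, and C the number completing. Completers are taken to be engaged.

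- As written: (R − C)/E
- Among the engaged: (E − C)/E
- Difference: (R − E)/E, that is, early leavers divided by engaged

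The two agree only if nobody leaves before attending three sessions.

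**Dropout: illustration.** R = 30 per condition is from the sample size rationale. The total of 8 dropouts is an assumption. It borrows the planned 25% loss at post-treatment (0.25 × 30 = 7.5, rounded up), although that figure is loss to outcome assessment and not treatment dropout. The split between early and later leavers is also assumed, and everyone else is taken to engage.

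| Early leavers | Engaged | As written | Among engaged | Difference |
|---|---|---|---|---|
| 0 | 30 | 8/30 = 26.7% | 8/30 = 26.7% | 0/30 = 0 |
| 4 | 26 | 8/26 = 30.8% | 4/26 = 15.4% | 4/26 = 15.4 points |
| 8 | 22 | 8/22 = 36.4% | 0/22 = 0% | 8/22 = 36.4 points |

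With total dropout held at 8, the two rates move in opposite directions as more of the departures come early. All dropouts over all randomized stays at 8/30 = 26.7% in every row.

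**Completion.** C enters both formulas. Because the number of sessions varies by participant and completion is not defined, neither version has a unique value yet.

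**Fidelity: does the CBT-I scale go above 2?** If 2 were the top score, an average of 2 would require every item to be 2. No item could then be 0, and the separate no-0 condition would do nothing. That condition has work to do only if scores above 2 can offset a 0. For example, with ten items (an assumed number) scored 0, 3, 3 and seven 2s, the average is (0 + 3 + 3 + 14)/10 = 2. So the rule's own structure implies scores above 2.

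**Fidelity: consequence.** Again assume ten items, and a score of 3. Nine items at 2 and one at 3 average (18 + 3)/10 = 2.1. That is not equal to 2, so the session fails as written. A session with every item at 3 fails too. Both pass under a floor of 2.

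**Health and Wellness.** Only two labels appear. If these are the only levels, no average can exceed acceptable, and the equality is coherent. If there is a higher level, the CBT-I problem carries over. The documents do not show which.

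**The case against.** The strongest reply is that the intent is plain. The dropout item runs in sequence: engagement first, then dropout over the engaged. Choosing that denominator suggests that dropout is counted among those people, and early leavers already appear as non-engaged. As a reading of intent this stands, and it makes the point a defect of wording and not evidence of a planned miscalculation. It does not remove the point, because the text sets the denominator and leaves the numerator open.

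On fidelity, adequacy is defined by outside roll-out criteria, so the phrase in the plan may be a loose paraphrase. The inference that scores above 2 exist also assumes that the no-0 condition was written to do something. Both remarks are fair, and they are why the change should wait for a check of the source. For Health and Wellness the objection succeeds: the documents do not establish a defect there.

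A reader might infer more than the text supports. One inference is that the dropout rate will exceed 100%. It can, but 14 early and 4 later leavers of 30 are needed to give 18/16 = 113%, which is 60% attrition, and nothing in the plan anticipates that. Another is that the fidelity pass rate always falls as ratings improve. That holds only once the mean rating is at or above 2; below it, better ratings can raise the share of sessions averaging exactly 2. Without the item count, top score and score distribution, no percentage of wrongly failed sessions can be given.

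**Conclusion.** The point holds at low severity. As written, the dropout ratio is not a proportion and overstates dropout among the engaged by early leavers over engaged. Under the assumed 8 dropouts of 30, the overstatement runs from 0 to 36 percentage points, depending on how many leave early. As written, the CBT-I fidelity rule fails sessions rated better than satisfactory, given the inference that scores above 2 exist. How many sessions this would affect cannot be judged from the documents.

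A reader might infer that the feasibility conclusion or the efficacy comparison is at risk. The documents do not support that. Hypothesis 1 is descriptive, no pass mark is attached to either figure, and no test, power figure or efficacy estimate changes.

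**What to change.** 1. Define the dropout rate as *the number of engaged participants who left before completing treatment, over the number engaged*. State what counts as completing treatment when the number of sessions varies by participant. Optionally, also report all dropouts over all randomized, which does not depend on the engagement cut.
2. Change the CBT-I fidelity cut to *at least 2*, keeping the no-0 condition, once this is confirmed against the cited roll-out criteria.
3. Check the Health and Wellness scale. If it has a level above acceptable, use *at least acceptable*; if not, leave the rule alone.

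The cost is a few words, a definition of completion and a look at two rating-scale sources. Data collection, tests and sample size do not change.
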